6.3 Study population

The study population is uncircumcised men ≥ 18 years accessing STI care regardless of their HIV status, at Bwaila STI clinic between April and September 2020 in Lilongwe Malawi. The population will also include healthcare workers at Bwaila STI and VMMC clinics and other key stakeholders. The other key stakeholders will MoH VMMC program officials, and the private sector such as the CDC, PSI and Jhpeigo.

6.4 Inclusion Criteria

The inclusion criteria will be as follows:

- Uncircumcised men ≥ 18 years accessing STI care regardless of their HIV status
- Willingness to participate in the study
- Willingness to provide informed consent

6.5 Exclusion criteria

Men with prior exposure to research activities who come for repeat STI visits

6.6 The RITE Intervention

The RITE intervention was developed solely based on literature. As such, based on results from the formative research, the content of the intensified health education will be designed to make it more setting specific.

6.6.1 Composition

The RITE intervention has been guided by the conceptual framework (figure 1) and Powell et al's refined compilation of implementation strategies [32].

Intensified Health Education (I)

Intensified health education will be more consistent and setting-specific education on VMMC incorporated into the routine STI/HIV health education provided at Bwaila STI clinic.

Currently, health education on VMMC at Bwaila STI clinic is offered once in the morning session – leaving out patients who come later to the clinic. The health education session combines education on HIV and STIs, usually offered by HIV testing counselor or clinic receptionists, and education on medical circumcision, offered by a VMMC mobilizer from the Bwaila VMMC clinic.

In this PhD study, we intend to make health education more setting specific and delivered better by conducting formative research to understand the views of men on VMMC with emphasis on men accessing STI care. In addition, we intend to intensify the education by conducting additional (more than one educational talk as per current standard) educational talks. The health talks will be delivered at Bwaila STI clinic – the recruitment point. The current format of the educational talks will be maintained but in addition, educational material on medical circumcision will be developed based on results from the formative research. The VMMC

mobilizer including the clinic receptionist and counselors will be trained on the educational material. We anticipate that the content of the health talk may involve the following fundamental information: description of VMMC, medical benefits of VMMC and addressing myths and misconceptions around VMMC among other topics. After the group education, men will be asked of their interest in circumcision individually by counsellors (during standard HIV testing) and clinicians as they receive care at the STI clinic.

Clinic Escorts (E)

Clinic escorts will be the act of escorting/accompanying a participant interested in VMMC from the STI clinic to the VMMC clinic to ensure linkage to care. We propose to use clinic escorts who will accompany men interested in VMMC from the STI clinic to the VMMC clinic to ensure that men are not lost in transit. Men may either undergo same day VMMC (if asymptomatic) or have an appointment for VMMC on a later date if symptomatic or if they have other viable reasons. Escorting patients is beneficial in linkage and retention in care and is policy in varied clinical settings [32]. Clinic escorts will be data clerks and clinic aides.

SMS Tracing (T)

SMS reminder tracing will be the act of reminding participants with a VMMC appointment about their date of procedure through short messaging service. This PhD study proposes to use SMS tracing to remind men who could not have same day VMMC of their appointment for VMMC. The content and frequency of the SMS messages will be guided by the findings from formative research however we have included a modifiable guide of the messages. Cell phone tracing is also a proven strategy for minimizing loss to follow-up and improving retention [33–35]

Transport Reimbursement (R)

Transport reimbursement will be refunding money used for transportation to the Bwaila district hospital for participants who undergo VMMC using standard Malawi government rates.

Transport reimbursement equivalent to US\$10 as stipulated by the National Health Sciences Research Ethics Committee (NHSRC) in Malawi, will be offered to all men who will undergo VMMC on the day of the procedure to minimize the opportunity cost. Incentives also have been shown to improve many medical outcomes [40, 41]. Eligible men will receive transport reimbursement when they undergo VMMC. Men who cannot have same day circumcision will receive a coupon to present on the day of the procedure for reimbursement. Documentation of the VMMC procedure will be confirmed in the VMMC clinic's procedures register before payment.

6.6.2 Implementation

The implementation will be guided by the NIRN stages of implementation framework.

Exploration

As detailed under the conceptual framework, we will conduct expert consultation meetings with key stakeholders including MoH, CDC, PSI, Jhpeigo and healthcare workers from Bwaila STI and VMMC clinics. The aim of the meeting will be understand the views of men of VMMC from the experts and identify the best way to conduct health education and the appropriate content to include in health education material in a STI clinic setting. This stage may last for one week.

Installation

This stage will be used for developing and endorsing educational material and the delivery methods. Necessary resources for the study will be mobilized. All staff (STI clinic and VMMC

clinic) will be trained by the investigator on the intervention. The clinic receptionist, VMMC mobilizer, counsellors and nurses will be specifically trained on the intensified health education material. This stage will be one week.

Initial Implementation (Pre-test)

This stage will be used to pre-test the intensified health education. We will use the lessons learnt from the pre-test to refine the educational material. This stage will also allow HCWs at the two clinics to internalize the intervention. Support to healthcare workers will be provided through supervision, retraining and constructive feedback. This stage may last about two weeks – one week for pre-testing and another week for making necessary modifications if necessary.

Full implementation

This will be full roll-out of our intervention. The intervention will have four implementation blocks (Appendix 1) that will be different combinations of the intervention components in an incremental manner. There will be one week of no intervention between interventions as a wash-out period. The implementation will be as follows: First we will observe the SOC VMMC referral process. In **block one**, we will introduce IHE which will then be maintained throughout the implementation period. Clinic escorts combined with IHE in **block two**. **Block three**, IHE, clinic escorts and SMS tracing will be combined. In **block four**, all intervention components will be combined including transport reimbursement to form the full intervention. Supportive supervision and constructive feedback will be maintained throughout the implementation period. Based on the sample sizes detailed below, we anticipate that each intervention block will last about 3-4 weeks.

6.1 Sampling

We will use purposive sampling to select experts or stakeholders involved in VMMC programs (MoH officials, HCWs and private sector officials) to attend the consultative meeting. Men who will participate in the surveys and focus group discussions will be purposively recruited and segmented by meaningful characteristics, such as age, marital status, religion or other factors that the experts think are vital. We will also use purposive sampling to select healthcare workers (HCWs) to participate in the in-depth interviews (IDIs) and surveys. No sampling techniques will be required for measurement of uptake of VMMC. The sample sizes and time points of measurements have been outlined in the sections below.

6.2 Data Collection

Overall, we will collect demographic characteristics for our study population. Among men accessing STI care, we will collect demographic data such as age, marital status, educational status and socioeconomic status. Additional data collected may include sexual history, HIV and ART status. Data will be collected using the routine electronic medical registry at Bwaila STI clinic and exported into a Microsoft Excel spreadsheet.

Objective 1: To compare uptake of voluntary medical male circumcision between the standard of care and the different combinations of the RITE intervention among men attending Bwaila STI clinic in Lilongwe Malawi

Uptake in this study will be the action of undergoing VMMC. Uptake of the intervention will be measured for each implementation block. Data on demographic characteristics including contact information, HIV history, sexual history and STI data will be collected for all participants from

the STI clinic using a routine clinical form through the electronic medical registry (EMR) (Appendix 2). We will collect data on the number of uncircumcised men offered VMMC and the number of men referred to the VMMC clinic from the STI clinic using study specific data collection form (Appendix 3). In addition the number of men who underwent VMMC will be collected from routine VMMC clinic registers using a study specific data collection form (Appendix 4). Data clerks and the VMMC mobilizer will collect these data on a daily basis from both clinics. SMS tracing attempts will be collected separately on a study-specific SMS tracing form (Appendix 5). The content of the SMS will be designed during the pre-test but we have included a draft of what the content may include (Appendix 5). The data will be collected and collated daily by a data clerk. Data will be entered into a Microsoft Excel spreadsheet by a data assistant.

Objective 1a: To compare time-to-uptake of voluntary medical male circumcision between the pre- and post-intervention periods among men attending Bwaila STI clinic in Lilongwe Malawi

Time-to-uptake will be the number of days from the day a participant is offered VMMC to the day they undergo VMMC. Data clerks will collect data on the date the participant is offered VMMC from the STI clinic using a study-specific data collection form (Appendix 3) while the date the participant undergoes VMMC will be collected from routine VMMC clinic registers on a daily basis and entered into Microsoft Excel.

Objective 1b: To assess factors affecting uptake of voluntary medical male circumcision among men attending Bwaila STI clinic in Lilongwe Malawi

We will collect data on demographic, sexual and HIV/ART will be collected from the Bwaila STI clinic electronic medical registry and exported to Microsoft excel spreadsheet. Data will be

exported on a weekly basis by a data assistant. We will use these covariates to assess factors affecting uptake of VMMC among men who will undergo VMMC.

Objective 2: To develop STI clinic setting-specific voluntary medical male circumcision educational material at Bwaila STI clinic in Lilongwe Malawi

To achieve this objective, firstly, we will collect data from the consultative meeting with key stakeholders outlined in the above sections as notes. The notes will be collected by the investigator and another note-taker. Data will be analyzed in real-time. The suggested content and delivery methods will be identified. Secondly, we will conduct a pilot of the intensified health education material and methods on men accessing care at Bwaila STI and collect more notes on possible ways to refine intensified health education. Any necessary refinements will be done and the intensified health education material and methods will be endorsed.

Objective 3: To assess the acceptability, appropriateness and feasibility of the RITE intervention among men and healthcare workers at Bwaila STI clinic in Lilongwe, Malawi.

Acceptability will be defined as the perception among men and HCWs that the RITE intervention is agreeable, palatable and satisfactory [36]. Appropriateness will be the perceived fit of the RITE intervention to address the problem of low uptake of VMMC among men and HCWs [36]. Feasibility will be the extent to which the RITE intervention will be successfully carried out at Bwaila STI clinic [36]. Acceptability, appropriateness and feasibility will be measured quantitatively using surveys and qualitatively using in-depth interviews (IDIs) and focus group discussions (FGDs). Acceptability and appropriateness will be measured before (at

baseline) and during implementation of our intervention for each implementation block.

Feasibility will be measured during implementation for each implementation block because it cannot be measured before exposure to the intervention [36]. A vignette (embedded in the data tools) on the RITE intervention will be read out to respondents to describe the intervention. Data on acceptability, appropriateness and feasibility will be collected using the following methods:

Surveys: For acceptability, we will use the acceptability of intervention measure (AIM), a tool designed by Weiner et al [37], to collect quantitative data for acceptability. The AIM uses Likert scales of four constructs which assess if an intervention is appealing, likeable, welcome and approved. For appropriateness, we will use the intervention appropriateness measure (IAM) to collect quantitative data for appropriateness [37]. The IAM uses a Likert scales of constructs which assess if an intervention is fitting, suitable, applicable, and a good match. For feasibility, we will used the feasibility of intervention measure (FIM) for feasibility Surveys [37]. The FIM uses a Likert scales of constructs which assess if an intervention is implementable, possible, doable, and easy to use. These tools have been slightly modified to suit the study setting.

Acceptability and appropriateness will be conducted at baseline and for each implementation block except for feasibility which cannot be assessed before exposure to the intervention (Appendix 6 - 9). Surveys data will be collected on electronic tablets through open data kit (ODK). Data clerks will administer surveys on an electronic tablet for the men while HCWs will self-administer the surveys. Each survey will to last approximately 10 - 20 minutes. Survey data will be downloaded from the tablets to a Microsoft Access password-locked database. IDIs and FGDs will complement the surveys.

In-depth interviews: IDIs will be conducted with HCWs from Bwaila STI clinic only. IDIs will

be ideal for HCWs because they are fewer in number, easier to reach and will provide a platform to explore in more detail if our intervention is practical for the clinic. IDIs will be conducted in the local language (Chichewa) by the investigator with the help of a qualitative researcher. We will conduct interviews with HCWs before implementation (baseline) and during implementation (during the last implementation block with the full RITE intervention) to explore implementation issues until saturation is reached. Each interview will last approximately 45 – 60 minutes. IDIs will be administered using an interview guide developed by the investigator in consultation with qualitative researchers are the University of North Carolina Project (UNC Project) in Malawi (Appendix 10).

Focus Group Discussions: FGDs will be conducted with the men only. FGDs will be ideal for the men because they will allow us to collect opinions from more men at one time compared to IDIs. Men will be purposively recruited and segmented by meaningful characteristics, such as age, marital status, religion or other factors that the experts think would influence what and how men may share information. FGDs will be conducted in Chichewa by the investigator with help from qualitative researchers. The FGDs will be administered using a guide developed by the investigator and qualitative researchers from UNC project (Appendix 11). Each FGD will have between 8 to 12 men. We will conduct two FGDs before implementation at baseline (appendix 11) and another two FGDs during implementation of the full RITE intervention only (appendix 11). Each FGD will be approximately 60 – 90 minutes. The IDIs and FGDs will complement the quantitative methods by exploring factors identified in surveys.

We will take notes and record the IDIs and FGDs. IDIs and FGDs will be translated to English during transcription. The investigator and one qualitative researcher will conduct the transcription and coding using Nvivo 14 S.E. in preparation for thematic analysis. We will

ensure intra-coder and inter-coder consistency by comparing codes. In case of inter-coder inconsistencies, a third person (socio-behavioural scientist) will conduct the coding (tiebreaker). We will collect demographic data from all respondents. A summary of methods is available in Table 1, Appendix 12.

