5.4.2 Specific objectives

1. To compare uptake of voluntary medical male circumcision between the RITE intervention and the standard of care among men attending Bwaila STI clinic in Lilongwe Malawi
 - a. To compare time-to-uptake of voluntary medical male circumcision between the RITE intervention and the standard of care among men attending Bwaila STI clinic in Lilongwe Malawi
 - b. To assess factors affecting uptake of voluntary medical male circumcision among men attending Bwaila STI clinic in Lilongwe Malawi
2. To develop STI clinic setting-specific voluntary medical male circumcision educational material at Bwaila STI clinic in Lilongwe Malawi
3. To assess the acceptability, appropriateness and feasibility of the RITE intervention among men and healthcare workers at Bwaila STI clinic in Lilongwe, Malawi.

- a. To assess the acceptability and appropriateness of the RITE intervention among men at Bwaila STI clinic in Lilongwe, Malawi

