Uptake will be calculated as a proportion - the number of men who will undergo VMMC divided by the number of uncircumcised men offered VMMC at the STI clinic. Uptake will be calculated for each implementation block. Uptake for each block will be compared against SOC using Student's T-test at $\alpha=0.05$ significance level and 95% confidence interval, assuming normal distribution.

Objective 1a: To compare time-to-uptake of voluntary medical male circumcision between the standard of care and intervention period among men attending Bwaila STI clinic in Lilongwe Malawi

Time-to-uptake of VMMC will be calculated as the number of days taken for an individual to undergo circumcision at the VMMC clinic from the day they were offered circumcision at the STI clinic. To compare time-to-uptake between SOC and the intervention blocks, we will conduct time-to-event analysis to estimate duration to circumcision and Kaplan Meier curves will be plotted and compared between SOC and implementation blocks. We will also study factors affecting time-to-uptake using cox regression.

Objective 1b: To assess factors affecting uptake of voluntary medical male circumcision among men attending Bwaila STI clinic in Lilongwe Malawi

We will assess factors affecting uptake of VMMC using logistic regression modeling. We will use univariate models to assess association. Covariates with $P<0.05$ and those based on expert knowledge of this topic will be fit into multivariate logistic regression models to control for confounders.

Objective 2: To develop STI clinic setting-specific voluntary medical male circumcision educational material at Bwaila STI clinic in Lilongwe Malawi

We will use thematic analysis approach for qualitative analysis of the consultative meeting notes. The notes will be coded and salient themes will be identified. The content and delivery methods will be deduced from the salient themes.

Objective 3: To assess the acceptability, appropriateness and feasibility of the adaptable RITE intervention among men and healthcare workers at Bwaila STI clinic in Lilongwe, Malawi.

We will use mixed methods to assess acceptability, appropriateness and feasibility. For acceptability, appropriateness and feasibility quantitative surveys, these outcomes will be

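### Objective 1b: the data section names circumcised men as the analysis set, where the planned logistic model of uptake cannot be fitted and which contradicts the rest of the plan

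*Combined protocol and SAP*

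**What the plan says.** The objective in 5.4.2 Specific objectives reads "To assess factors affecting uptake of voluntary medical male circumcision among men attending Bwaila STI clinic". The same population heads the Objective 1b paragraphs in 6.2 Data Collection and in the Data Analysis text, which sits under 6.3 Sample Size Calculation and Justification.

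The paragraph in 6.2 Data Collection then says that the demographic, sexual and HIV/ART data will be used to "assess factors affecting uptake of VMMC among men who will undergo VMMC". The same section defines the outcome: "Uptake in this study will be the action of undergoing VMMC".

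The Data Analysis text for Objective 1b says "We will assess factors affecting uptake of VMMC using logistic regression modeling", and then "We will use univariate models to assess association". Covariates with P<0.05, or chosen on expert knowledge, go into a multivariate model. Apart from its heading, that paragraph does not say which men enter the model.

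For Objective 1, the same text calculates uptake as the number circumcised "divided by the number of uncircumcised men offered VMMC at the STI clinic".

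**The concern.** A logistic model of uptake compares men who took up VMMC with men who did not. A set defined by having undergone VMMC contains only the first kind. The sentence in 6.2 Data Collection is the only place in the supplied text that links the Objective 1b covariates to a stated group of men other than the objective's own wording, and that group cannot support the model.

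An analyst who follows the sentence gets no odds ratios. An analyst who sets it aside must choose a replacement, and the plan leaves several open: men attending the clinic, men offered VMMC, or men referred to the VMMC clinic. A covariate association answers a different question in each. Factors affecting uptake are also a named part of the second paper under Proposed publications, so the set should be fixed before the data are seen.

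**Working it through.** The plan gives no sample size or power for Objective 1b, so there is no stated figure to reproduce. The check has three parts.

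**1. Can the model be fitted in the set named?** Let y = 1 if a man undergoes VMMC and 0 otherwise. In a set of n men who all have y = 1, the intercept-only log-likelihood at intercept b is −n·log(1 + e^(−b)). It rises towards 0 as b grows and never reaches a maximum. For example, with n = 259:

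| b | log-likelihood |
|---|---|
| 1 | −81.1 |
| 5 | −1.74 |
| 10 | −0.012 |
| 20 | −0.0000005 |

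Adding a covariate does not help. For any slope, a large enough intercept brings the log-likelihood as close to 0 as one likes, so the slope is not identified. This holds for every n.

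**2. Numerical confirmation.** The number of men is the plan's own, from 6.3 Sample Size Calculation and Justification: 27 × (1 − 0.28) = 19.4, taken as 19 uncircumcised men per day; 380 per month (19 × 20 days); 380 × 6 = 2280. That figure reproduces. It counts men visiting, not men offered VMMC, and serves only as a working size. The same section says incidence data are unavailable, so uptake of 5%, 10%, 20% and 30% is assumed. So is one covariate with a true log-odds ratio of 0.4. One simulated data set per rate gave:

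| Assumed uptake | Circumcised, of 2280 | Model on all men: log-odds ratio (SE) | Model on circumcised men only |
|---|---|---|---|
| 5% | 124 | 0.45 (0.093) | singular matrix |
| 10% | 259 | 0.33 (0.068) | singular matrix |
| 20% | 473 | 0.42 (0.054) | singular matrix |
| 30% | 705 | 0.38 (0.047) | no convergence; slope −6.0 (SE 226) |

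The model was estimable every time on the full set and never on the circumcised men alone.

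**3. Which set does the rest of the plan imply?**

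| Place | What it implies |
|---|---|
| 5.4.2, and both later Objective 1b headings | men attending the STI clinic |
| 6.2 Data Collection, Objective 1 | demographic, HIV, sexual-history and STI data on all participants |
| 6.2 Data Collection, Objective 1b | weekly registry export, with no filter by circumcision status stated |
| Data Analysis, Objective 1 | denominator is uncircumcised men offered VMMC |
| Data Analysis, Objective 1b | logistic model, not restricted to circumcised men |
| 6.2 Data Collection, Objective 1b, sentence on use of covariates | circumcised men only |

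Only the last row names a set with a constant outcome. The others are compatible with a set containing both outcomes, but they do not agree on a single one.

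**Block.** 6.6.2 Implementation has standard of care followed by four blocks in sequence, each with a different combination of components. 6.5 Limitations and anticipated challenges calls seasonality a well-known confounder. The Objective 1b covariates are demographic, sexual and HIV/ART, and neither Objective 1b paragraph names block. A man's block fixes both what he was offered and when.

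**The case against.** The best defence is that this is one loosely worded phrase. It closes a sentence about how covariates will be used, in a section on collecting data. The objective, both headings and the analysis paragraph carry no such restriction, and the choice of a logistic model presupposes both outcomes. If anyone did follow the phrase, the model would fail visibly and would not bias a result unnoticed. A summary of methods is also cited as Appendix 12. It is not in the supplied text and may state the set.

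Much of this stands. A reader might infer that Objective 1b cannot be answered, or that the comparison group would be lost because covariates are compiled only for circumcised men. The documents do not support either reading. Covariates are to be collected on all participants, the export has no stated filter, and the restrictive phrase governs use, not collection.

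The defence does not remove the contradiction. Nothing in the supplied text corrects the phrase, and setting it aside still leaves attending, offered and referred men as candidates. Objective 1 fixes its denominator; Objective 1b does not.

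**Conclusion.** The point holds as an internal contradiction on the Objective 1b analysis set. In the set that 6.2 Data Collection names, the outcome is constant and the planned logistic regression cannot be fitted. That conclusion follows from the plan's definition of uptake and depends on no assumed rate; the uptake rates and covariate effect above only illustrate it. The plan's remaining text points to a wider set in which the model is estimable.

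The consequence is limited. This is a sub-objective, the Objective 1 comparison of uptake is unaffected, and no loss of data is shown. No meaningful number of men lost can be given, because the plan states no expected uptake and the failure is the same at any size. The absence of block from the named covariates is a smaller, related gap that can be closed in the same edit.

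**What to change.** 1. In 6.2 Data Collection, Objective 1b, replace the closing phrase so that the covariates are used for all uncircumcised men offered VMMC, whether or not they go on to be circumcised.
2. In the Data Analysis text for Objective 1b, state that the univariate and multivariate logistic models are fitted to that set, with VMMC yes or no as the outcome. This matches the Objective 1 denominator.
3. Include study block (standard of care and blocks one to four) as a fixed term, kept in the model whatever its univariate P value. Blocks run one after another at a single clinic, so this term adjusts for intervention and calendar time together and does not separate them.
4. If Appendix 12 states the set, bring it into line.

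The cost is two or three sentences. No new data are needed: covariates are already planned for all participants, Objective 1a already records each man's offer date and circumcision date, and block follows from the offer date. This assumes that the registry, the offer form and the VMMC register can be linked man by man, which the planned Cox regression under Objective 1a already requires.
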